Section 5, Table 4 (Time and Events)	N/A	Adds a -1 day window to D8 and D15 assessments	To allow flexibility in patient schedules
Section 7.2.1 (Adverse Events)	N/A	Now includes standard language describing examples of AE classification	To align with current NU protocol template
Section 11.6.2 (Protocol Deviations)	N/A	Now includes standard language describing Reportable New Information (RNI)	To align with current NU protocol template
Throughout	N/A	Corrects minor grammatical/typographical errors and formatting	Administrative change
Amondmont 9 December 9, 2049			
SRC-approved on March 3, 2019			
Section(s) Affected	Prior Version	Amendment 9 Changes	Rationale
Cover Page and	Protocol version dated July	Updates version date to	Administrative update

Throughout	5, 2019 (Amendment 8)	December 9, 2019 (Amendment 9)	
Table of Contents	N/A	Updates page numbers	Administrative update
Inclusion Criterion 3.1.4	Required creatinine clearance of ≤ 30 mL/min	Requires creatinine clearance of ≥ 30 mL/min	Corrects typographical error. Replaces "≤ 30 mL/min" with "≥ 30 mL/min"
Section 7.2.4 (UPIRSO) Section 7.2 (Expedited Reporting of SAEs) Section 11.6 (Adherence to the Protocol) Section 11.7 (Amendments to the Protocol) Section 11.10 (Publication Policy)	N/A	Updates standard language to align with new Northwestern University protocol template	Administrative update
Section 9.3.2 (Tissue Collection)	Construction of the TMA will require minimum of five unstained slides of tissue for proper analysis.	Construction of the TMA will require 1.0 to 1.5 mm punch cores for proper analysis.	Updates for flexibility in tissue collection procedures
Appendix E (Protocol History of Changes)	N/A	Adds SRC-approval date for protocol amendment 8 Summarizes revisions for protocol amendment 9	Administrative update

Amendment 10 – May 22, 2020

Section(s) Affected	Prior Version	Amendment 9 Changes	Rationale
Cover Page and Throughout	Protocol version dated December 9, 2019 (Amendment 9)	Updates version date to May 22, 2020 (Amendment 10)	Administrative update
Table of Contents	N/A	Updates page numbers	Administrative update
Section 4.1.2 (Lenalidomide); Section 4.1.3 (Treatment Regimen & Supportive Therapies); Table 1b	The dose should be adjusted in patients with moderate or severe renal impairment Table heading:	Addition of bolded text: The dose and schedule should be adjusted in patients with moderate or severe renal impairment Table heading:	Clarification. Clarifies language to align with the contents of Table 1b, which describes the adjusted dose and schedule for lenalidomide for patients with moderate
	Dose	Dose and Schedule	or severe renal impairment.
	N/A	Addition of bolded text in footnote.	Clarification.
Table 1b		¹ Creatinine clearance (CrCl) will be measured and calculated prior to	Adds footnote 1 to Table 1b to clarify the process to calculate creatinine

		initiating each cycle as described in the Study Procedures Table in Section 5.0. (Refer to Appendix D for instructions on calculating CrCl). The dose of lenalidomide will be adjusted per Table 1b. Any questions regarding dose calculations/ adjustments should be directed to the Lead PI.	clearance to determine lenalidomide dosing.
Section 5.0 (Study Procedures)	¹⁶ Romidepsin will be administered intravenously on days 1, 8, and 15 of each cycle. The dose for the first 2 cycles (6 doses total) will be 10 mg/m2; in some cases, patients may be escalated to a dose of 14 mg/m2 for remaining cycles (see Section 4.1.1 for specific criteria). A window is allowed for romidepsin infusion visits (within ±3 days of day 1, and within +3 days of days 8 and 15).	Addition of bolded text to footnote: ¹⁶ Romidepsin will be administered intravenously on days 1, 8, and 15 of each cycle. The dose for the first 2 cycles (6 doses total) will be 10 mg/m2; in some cases, patients may be escalated to a dose of 14 mg/m2 for remaining cycles (see Section 4.1.1 for specific criteria). A window is allowed for romidepsin infusion visits (within ±3 days of day 1, and within -1 to +3 days of days 8 and 15).	Corrects discrepancy. Modifies footnote 16 to revise the window for D8 and D15 to be -1 to +3 days to align with footnote 11. Footnote 11 states that, "Day 8 and 15 each have a window of -1 to +3 days."
Section 5.0 (Study Procedures)	N/A	Adds "creatinine clearance check" to the Study Procedure's Table with a corresponding footnote. Addition of bolded text below:	Clarification. Clarifies the process to calculate creatinine clearance to determine

			Less - Relational de la stational	
		²⁰ Creatinine clearance will be measured and calculated prior to initiating each cycle (Refer to Appendix D for instructions on calculating creatinine clearance). The dose of lenalidomide will be adjusted per Table 1b. Any questions regarding dose calculations/ adjustments should be directed to the Lead PI. Refer to Section 4.1.3 for additional information.	lenalidomide dosing.	
Appendix C; Appendix D	Appendix C and Appendix D did not appear in the Table of Contents. Appendix D did not have a title.	Revises formatting and adds title to appendix so both appendices appear in the Table of Contents appropriately.	Administrative update	
Appendix E (Protocol History of Changes)	N/A	Adds SRC-approval date for protocol amendment 9. Summarizes revisions for protocol amendment 10.	Administrative update	
Throughout	N/A	Minor formatting adjustments.	Administrative update	
Amendment 11 – November 17, 2021				
Section(s) Affected	Revision		Rationale	
Cover page & Throughout	Updates the principal investigator from [name] to [name] and provides contact information		Administrative revision	
Throughout	Editorial revisions: Updates the protocol version/date and Appendix E (Protocol History of Changes)		Administrative revision

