Objectives	 Primary Evaluate the efficacy of romidepsin plus lenalidomide in patients with PTCL; this will be done by evaluating the objective response rate by Cheson criteria. Secondary objectives: Evaluate safety (as defined by frequency and severity of toxicity events). Further evaluate efficacy as measured by PFS and OS measured at 1 and 3 years after beginning treatment. Further evaluate efficacy as measured by duration of response and time to first cytotoxic chemotherapy. Exploratory objectives: Further evaluate the use of NM PET/CT vs CT imaging in PTCL. Validate a new prognostic model for newly diagnosed PTCL. 		
	3. Investigate the tumor immunohistochemical profile to identify potential biomarkers associated with prognosis and treatment response		
Study Population	Up to 35 adult patients with previously untreated PTCL (see specific histologic subtypes in Schema and Section 3.0) may be enrolled to obtain 20 evaluable patients.		
Treatment Plan	 Patients will receive treatment in cycles defined as 28 days each: Romidepsin 10 mg/m² IV on days 1, 8, and 15 of each cycle (dose escalated to 14 mg/m² if tolerated first 6 doses) Lenalidomide 25 mg PO daily days 1- 21 of each cycle Patients may receive treatment for up to 1 year (unless discontinued prior to that for progression of disease, intolerable toxicity, or withdrawal of consent) 		
Statistical Methodology	The study will analyze n=20 evaluable patients. This will allow us to estimate the underlying true response rate with a half width of an approximate 95% confidence interval equal to 1.96x0.5/sqrt(20) = 1.96x0.11 = 0.22.		

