4.4 Duration of Therapy & Early Withdrawal

Treatment may continue for up to one (1) year or until any of the following occur, resulting in early withdrawal from study treatment (or in some cases withdrawal from the study as a whole):

- disease progression
- inter-current illness that prevents further administration of treatment
- unacceptable toxicity
- patient decides to withdraw from study treatment (or study as a whole)
- general or specific changes in the patient's condition render the patient unacceptable for further treatment in the judgment of the treating investigator

Note: Patients who have not achieved PR or CR after 4 cycles should continue to be treated on the current protocol only if they have SD (i.e., not PD), AND if they do not have other options available that would present a more favorable risk/benefit ratio.

Patients will be removed (withdrawn) from study therapy for any of the criteria listed above. The PI and the Quality Assurance Monitor (QAM) at NU is to be notified of such events; the reason(s) for removal and the date the patient was removed are to be documented in the appropriate electronic case report form (eCRF). The patient should be followed as described below in Section 4.5.

Patients who withdraw consent from the study as a whole will be noted to have withdrawn from both treatment and any further follow-up.

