4.5 Duration of Follow Up

Once patients are off treatment for any reason, they will have a final off-treatment visit approximately 30 days post-last dose of study therapy. Thereafter, they will be followed with at least one clinic visit every 3 months for up to 1 year from start of treatment, then every 6 months up to 3 years from start of treatment (or until death, whichever occurs first). Patients removed from treatment for unacceptable adverse events will be followed until resolution or stabilization of the adverse event.

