4.6 Patient Replacement

Any patient who is registered to the study and then withdrawn without receiving any study treatment may be replaced. Any patient who completes fewer than 2 total cycles of therapy and is withdrawn for any reason except POD or toxicity will still be considered evaluable for toxicity endpoints but will not be evaluable for efficacy endpoints; for the purpose of efficacy endpoints, another patient may be added to the accrual goal with the approval of the Data and Safety Monitoring Committee (DSMC) at NU.

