10.2 Secondary Endpoints

To evaluate the safety of the combination of romidepsin and lenalidomide, the endpoint will be the frequency and severity of toxicity events using the NCI CTCAE v 4.03. All

adverse events will be summarized as to type, severity, frequency, timing and attribution. Descriptive frequencies and proportions will be used for this analysis.

To further evaluate efficacy of the combination of romidepsin and lenalidomide, the endpoint will be progression-free survival (PFS) and overall survival (OS) at 1 and 3 years after start of treatment as well as the duration of response from start of therapy, defined per Cheson criteria. Kaplan-Meier curves will be determined for progression-free survival and overall survival and the one- and three-year point on this curve, along with 90% confidence limits. Duration of response will be summarized by descriptive statistics in responders (mean, median, range).

To evaluate the delay to cytotoxic chemotherapy, the endpoint will be time to first cytotoxic chemotherapy (TTFCC) from start of treatment. This will be summarized by descriptive statistics (mean, median, range).

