Cover Page	Listed [name] as the Biostatistician	Updates to [name] as the new Biostatistician	Administrative update to account for staffing change		
Cover Page and Throughout	Coordinating Center was listed as the Clinical Research Office (CRO) at Northwestern	Updates the name of the coordinating center to the Clinical Trials Office (CTO) at Northwestern	Administrative update to account for a change in the coordinating center's name; the coordinating center itself will remain the same.		
Study Summary, Section 1.4 (Study Rationale), Section 3.0 (Patient Eligibility), and Section 10.0 (Statistical	Listed an accrual goal of 32 evaluable subjects	Updates to an accrual goal of 20 evaluable subjects and provides a new statistical plan in Section 10.0.	The study has been slow to accrue, and reducing the sample size will increase the feasibility of completing the trial in a timely manner.		

Considerations)			Modification requested by the lead site after receiving support from Celgene to reduce sample size.
Section 4.0 (Treatment Plan)	N/A	Adds the following: With PI approval, dose modifications (interruptions and reductions) may be permitted for any grade AE deemed intolerable by the patient, or per treating investigator discretion (with PI approval) if thought to be in the best interest of the patient.	Modification requested by the DSMC to align with best interests of participating patients.
Section 4.6 (Patient Replacement)	Stated: Any patient who completes fewer than 2 total cycles of therapy and is withdrawn for any reason except POD or toxicity will still be considered evaluable for toxicity endpoints; however, for the purpose of efficacy endpoints, another patient may be added to the accrual goal with the approval of the Data and Safety Monitoring Committee (DSMC) at NU.	Updates language to include the bolded text: Any patient who completes fewer than 2 total cycles of therapy and is withdrawn for any reason except POD or toxicity will still be considered evaluable for toxicity endpoints but will not be evaluable for efficacy endpoints ; for the purpose of efficacy endpoints, another patient may be added to the accrual goal with the approval of the Data and Safety Monitoring Committee (DSMC) at NU.	Language clarification requested by the Quality Assurance Monitor to clarify replacement of non- evaluable patients

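### Section 4.6 drops treated patients withdrawn before 2 cycles for reasons other than progression or toxicity from OS, PFS and TTFCC, not only from response

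*Combined protocol and SAP*

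**What the plan says.** Section 4.6 (Patient Replacement) covers a patient who "completes fewer than 2 total cycles of therapy and is withdrawn for any reason except POD or toxicity". Such a patient "will still be considered evaluable for toxicity endpoints but will not be evaluable for efficacy endpoints", and another may be enrolled in their place with DSMC approval. Appendix E logs these words as an Amendment 8 change. They match the current Section 4.6, so the rule is in force.

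The term *efficacy endpoints* is the heading of Section 6.2. Below it stand the response categories, PFS (6.2.5), OS (6.2.6), duration of response (6.2.7) and TTFCC (6.2.8). The Study Summary also treats PFS and OS as efficacy measures and says of the others: "Further evaluate efficacy as measured by duration of response and time to first cytotoxic chemotherapy".

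PFS, OS and TTFCC are all timed from the start of treatment. Section 4.5 continues after treatment stops, whatever the cause: "Once patients are off treatment for any reason, they will have a final off-treatment visit", followed by clinic visits up to 3 years from start of treatment or death. Section 10.2 plans Kaplan-Meier estimates at 1 and 3 years with 90% limits for PFS and OS, and a mean, median and range for TTFCC. It names no analysis population for any of them.

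**The concern.** A two-cycle condition can be defended for response, because a patient who leaves that early may never have a post-baseline scan. That argument does not carry over to OS or TTFCC. A date of death or of first chemotherapy can be known whether or not a scan was done, and the patient has been at risk since the first dose.

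The withdrawal reasons that trigger the exclusion are unlikely to be unrelated to outcome. Section 4.4 lists "inter-current illness that prevents further administration of treatment", the patient's own decision, and the investigator's judgment that the patient's condition no longer permits treatment. Section 3.1.3 enrols patients aged 60 or over, and younger patients with a CIRS score of at least 6 or judged ineligible for cytotoxic chemotherapy. In such a population, some who leave for these reasons may die soon afterwards. Others may move to chemotherapy without recorded progression, and these could have the shortest TTFCC in the trial. Both kinds of early event would be missing from the endpoints meant to capture them.

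**Working it through.** **Scope of the rule.** Three conditions must all hold: at least some treatment received, fewer than 2 cycles completed, and withdrawal for a reason other than progression or toxicity. The consequence is stated for efficacy endpoints without limit. Sections 6.2.5 to 6.2.8 and 10.2 contain nothing that restores these patients, and no other section confines the rule to response.

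**Figures in the plan.** The plan gives no figure for these time-to-event endpoints. Its one precision figure concerns response and reproduces: 1.96 × 0.5/√20 = 0.219, stated as 0.22.

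**How many patients.** Section 3.0 allows up to 35 accrued to obtain 20 evaluable, so at most 35 − 20 = 15 treated patients could be excluded. The documents give no expected number.

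**OS, illustration.** Assume 12 of 20 evaluable patients are alive at 1 year and k excluded patients all died within the year. All-treated 1-year OS is 12/(20 + k):

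- k = 0: 12/20 = 60.0%
- k = 1: 12/21 = 57.1%
- k = 2: 12/22 = 54.5%
- k = 3: 12/23 = 52.2%

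Each excluded early death is therefore worth about 2 to 3 points.

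**OS, other starting values.** Section 1.1 gives a median survival of about 3 to 4 years. If survival is exponential (an assumption), 1-year OS is 0.5^(1/3) = 0.794 to 0.5^(1/4) = 0.841. Then 20 × S/(20 + k) gives 0.756 to 0.801 for k = 1 and 0.690 to 0.731 for k = 3. If only half of the 3 excluded patients die within the year, the result is (20 × S + 1.5)/23 = 0.755 to 0.796.

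**The opposite case.** If all k excluded patients are alive at 1 year, the 60% becomes 13/21 = 61.9%, 14/22 = 63.6% or 15/23 = 65.2%. The direction depends on who leaves.

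**TTFCC, illustration.** Assume 20 exponential times with a true median of 8 months (scale 8/ln 2 = 11.54) and k excluded patients who start chemotherapy at 0.5 to 2 months, well below the middle of the sample. The expected j-th smallest of 20 such times is 11.54 times the sum of 1/i for i from 21 − j to 20. The factors are 0.578, 0.669 and 0.769 for j = 9, 10 and 11. Adding k early times shifts which of these form the median:

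- k = 0: mean of j = 10 and 11, 11.54 × 0.719 = 8.3 months
- k = 1: j = 10, 11.54 × 0.669 = 7.7 months
- k = 2: mean of j = 9 and 10, 11.54 × 0.623 = 7.2 months
- k = 3: j = 9, 11.54 × 0.578 = 6.7 months

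Simulation of 20,000 samples gave the same four values.

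**PFS.** Section 6.2.5 counts progression only. An early death without progression is not a PFS event under that definition, so excluding the patient removes time at risk and any later progression. No direction of bias follows from this.

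**The case against.** The strongest reply is that the rule was never meant to reach survival. It sits in a section on replacement, Appendix E describes it as a clarification for replacing non-evaluable patients, Section 10.1 ties the 20 evaluable patients to the response rate, and the definitions in 6.2.5 to 6.2.8 carry no two-cycle condition. That may well be the intention. But the text says efficacy endpoints, Section 6.2 defines them to include these three, and no passage says otherwise. An analyst following the document would exclude the patients.

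Size is the second reply. The 90% half-width for 60% with n = 20 is 1.645 × √(0.6 × 0.4/20) = 0.18, against shifts of 3 to 8 points. These are descriptive secondary endpoints with no decision rule, and adding a patient needs DSMC approval. This limits the importance of the point. It is not a reason to keep an avoidable exclusion.

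A reader might infer three stronger things that the documents do not support:

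- **That everyone leaving before 2 cycles is dropped.** The exception is explicit: patients withdrawn for progression or toxicity stay in every endpoint, with their deaths and chemotherapy starts.
- **That every early death from another cause is dropped.** Section 4.4 does not list death as a withdrawal reason, so how a death on treatment is classed is unstated. The clear case is a patient first withdrawn, for example for intercurrent illness, who then dies.
- **That correcting this needs no further data.** Survival follow-up is specified, but the follow-up column of Table 4 schedules neither imaging nor concomitant medications, and its footnote ties follow-up to survival endpoints. Later progression and chemotherapy dates may not be collected for every early leaver.

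**Conclusion.** The point holds within these limits. As written, Section 4.6 removes treated patients from OS, PFS and TTFCC when they leave before 2 cycles for a reason other than progression or toxicity, although they are followed for survival. For OS and TTFCC this conditions the estimate on a post-baseline event and can make it too favourable if these patients do worse than the rest. For PFS the loss is of time at risk and later progressions, and an upward bias is not shown.

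The illustrative size is about 2 to 3 points of 1-year OS per excluded early death, starting from an assumed 12 of 20 alive. For TTFCC it is about half a month of median per excluded early switch, under an assumed exponential median of 8 months. Both rest on assumed outcomes for the excluded patients, and their number is unknown. This shows what the rule permits. It does not show that a reported result is wrong.

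**What to change.** In Section 4.6, limit the consequence to response: these patients are *not evaluable for response*, in place of efficacy endpoints generally. Replacement for the response analysis can stay as it is.

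In Section 10.2, add that OS, PFS and TTFCC are analysed in all patients who received at least one dose of study drug, from start of treatment. This is the population that Section 6.1 already uses for toxicity. Patients who are lost or withdraw consent are censored at last contact, or at last disease assessment for PFS. Summarise TTFCC by Kaplan-Meier, because the planned mean, median and range cannot handle censored times.

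The cost is a few sentences. OS and TTFCC may come out slightly less favourable, and some early leavers will be censored early for PFS and TTFCC where later imaging or chemotherapy data are not collected.

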4.1.2 Lenalidomide

Lenalidomide will be given orally (PO) at a dose of 25 mg daily on days 1-21 of each 28 day cycle. NOTE: The dose and schedule should be adjusted in patients with moderate or severe renal impairment who are enrolled on the study (creatinine clearance < 60 mL/min). Please refer to Table 1b below for details. Lenalidomide should be taken at approximately the same time each day (preferably in the morning) with water. Lenalidomide capsules may be taken with or without food. Patients will be instructed to not crush, chew or open capsules. Only enough pills for 1 cycle may be dispensed at one time (prior to the start of each cycle). On days where patients will have romidepsin infusion, it does not matter whether lenalidomide is taken before or after the IV infusion.

If a dose of lenalidomide is missed, it should be taken as soon as possible on the same day. If it is missed for the entire day, it should not be made up (i.e. patients should not take 2 doses the following day). Patients will be given a mediation diary on which to record all doses taken, missed, or skipped. This diary will be reviewed with study staff during visits prior to the start of each new cycle (before medication for upcoming cycle is dispensed).

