4.1.3 Treatment regimen & supportive therapies

Table 1 below summarizes the treatment regimen and recommended supportive therapies for patients on this trial.

Agent	Recommended Premedications ¹	Dose	Route	Schedule ³	Duration				
Domidencin ²	30 min prior: $5-HT3 \text{ receptor}$ antagonist4 Dexamethasone 10 10 mg/m^2 IVDays 1, 8, 1 year or 								
Romidepsin-	antagonist⁴ Dexamethasone 10 mg IVPB	14 mg/m²	IV	Days 1, 8, 15	1 year or until POD				
LenalidomideNone25 mg5poDaily Days 1-2151 year or until POD ¹ Premedication protocol is for romidepsin infusions and includes recommended agents									
¹ Premedication and trea ² The parameters pati ³ Each cycle will and with ⁴ The recommen ⁵ The dose and s severe renal imp	protocol is for romidepsin doses; similar alternate r ting investigator. s specified in the shaded ent tolerates 2 or more cy be 28 days; romidepsin ir hin +3 days of days 8 and ded agent/dose is Zofran schedule of lenalidomide s pairment, as detailed in Ta	infusions medication boxes repr ccles (6 tot nfusions sh 15. 16 mg IVF should be able 1b be	and incluc s may be resent opt al doses) nould occu PB or equi adjusted f low.	les recommend given at the dis ional dose incr at 10 mg/m ² ur within ±3 day ivalent. or patients with	ded agents scretion of the ease if rs of day 1, moderate or				

-	Table	1a:	Treatment	Regimen
---	-------	-----	-----------	---------

Table 1b: Lenalidomide Dose Adjustments for Patients with Renal Impairment

Category	Renal Function	Dose and Schedule
Moderate	Creatinine clearance 30-60 ml/min ¹	10 mg daily (Days 1-21)
Severe	Creatinine clearance < 30 ml/min	15 mg every other day (Days 1, 3, 5, 7, 9,
	(not requiring dialysis) ¹	11, 13, 15, 17, 19, and 21)

¹ Creatinine clearance (CrCl) will be measured and calculated prior to initiating each cycle as described in the Study Procedures Table in Section 5.0. (Refer to Appendix D for instructions on calculating CrCl). The dose of lenalidomide will be adjusted per Table 1b. Any questions regarding dose calculations/adjustments should be directed to the Lead Pl.

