- ²⁰ Creatinine clearance will be measured and calculated prior to initiating each cycle (Refer to Appendix D for instructions on calculating creatinine clearance). The dose of lenalidomide will be adjusted per Table 1b. Any questions regarding dose calculations/adjustments should be directed to the Lead PI. Refer to Section 4.1.3 for additional information.

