3.2.2 (Exclusion	Corticosteroids were	Adds clarification that	Clarification – prior language
Criteria);	listed as being generally	corticosteroids are permitted	was unclear whether
4.3.2 (Permitted	excluded in eligibility	on study to treat any	corticosteroids of any type

Concomitant	criteria, and were not	condition other than PTCL.	were excluded, rather than
Medications);	listed in concomitant	Corticosteroids for PTCL are	steroids to treat PTCL
Concomitant	medications	treatment, but are permitted	
Medications)		prior to treatment for 10 or	
	Evoluted chamatharapy	fewer days	Clarification for simplicity
3.2.3, 3.2.10 (Exclusion	and high QT "within 4	high QT"≤ 28 days" prior to	Clarification for simplicity
Criteria)	weeks" prior to	registration	
326 (Exclusion	registration	Expands CNS (central	Clarification
Criteria)		nervous system)	Clamouton
4.0 (Treatment Plan);	Allowed a cycle window	Allows cycle window of ±3	Allows greater flexibility for
4.1.3 (Treatment regimen & supportive	of ±1 business day	days	VISItS
therapies); 5.0 (Study			
Procedures #10)	Detiente mou he	Detionto may be appolated	Clarification only a drug
4.4.4 (Demidensin)	escalated to 14mg/m ²	to 14mg/m ² romidepsin if	related AE would preclude
	romidepsin if they don't	they don't have drug-	patients from escalating in
4 1 1 (Romidensin) [.]	Recommended pre-	related grade 3-4 AE's Pre-medications are listed	dose An equivalent dose is
4.1.3 (Treatment	medications are Zofran	as Zofran 16mg and	recommended (rather than
regimen & supportive	16mg and	dexamethasone 10mg (or	saying "similar agent", which
(Recommended	(or similar agents)	equivalent)	avoid higher doses that may
Concomitant			prolong QTc (e.g. kytril > 2mg)
Medications Include);	"Romidensin infusions	"Romidensin infusions	Allows greater flexibility on day
4.1.3 (Treatment	should occur within 1	should occur within ±3 days	1 (to align with cycle windows),
therapies); 5.0 (Study	business day of days 1,	of day 1, and within +3 days	but maintains appropriate
Procedures #10,15)	8, and 15	or days 8 and 15.	window between infusions.
	Table 1b: "Dose	Table 1b: "Lenalidomide	Clarification – previously
113 (Treatmont	Adjustments"	Dose Adjustments"	unclear which drug was to be
regimen & supportive	Table 1b: severe renal	Table 1b: severe renal	Discrepancy – CrCl = 30
therapies);	impairment defined as	impairment defined as CrCl	previously fell into both
	CrCl ≤ 30	< 30	moderate and severe categories

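### Section 4.1.2 and Table 1b give different lenalidomide doses at a creatinine clearance of exactly 60 mL/min (25 mg against 10 mg daily)

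*Combined protocol and SAP*

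**What the plan says.** Section 4.1.2 gives the standard regimen: "Lenalidomide will be given orally (PO) at a dose of 25 mg daily on days 1-21 of each 28 day cycle". A note then calls for a changed dose and schedule in patients with "moderate or severe renal impairment who are enrolled on the study (creatinine clearance < 60 mL/min") and points to Table 1b for the particulars.

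Table 1b, in section 4.1.3, has two rows. The moderate row reads "Creatinine clearance 30-60 ml/min" and carries "10 mg daily (Days 1-21"). The severe row covers values below 30 mL/min.

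The check recurs throughout treatment. Footnote 20 to the Time and Events table in section 5.0 says: "Creatinine clearance will be measured and calculated prior to initiating each cycle". That footnote and footnote 1 to Table 1b both make Table 1b the basis for adjustment and direct questions about dose calculation to the Lead PI. Footnote 5 to Table 1a relies on the same terms, moderate and severe impairment, without giving a cut-off.

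Appendix D gives the clearance equations. No section says how the calculated value is to be rounded.

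Appendix E records that Amendment 10 edited the sentence in 4.1.2 and 4.1.3 and the heading of Table 1b, with the reason "Clarifies language to align with the contents of Table 1b".

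**The concern.** Section 4.1.2 uses a strict inequality, so a patient at 60 mL/min is not among those to be adjusted and stays on 25 mg. Table 1b writes its moderate band as a range ending at 60, so the same patient falls in the band and receives 10 mg. Moderate impairment thus has two definitions in the current text.

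The rule is applied before every cycle, in a population that is mostly aged 60 or over or selected for comorbidity, with entry allowed down to 30 mL/min. Values near 60 are therefore plausible. At the boundary, two sites that each follow the protocol could give doses that differ 2.5-fold, and a monitor would have no firm basis for deciding which one departed from it. What is at stake is consistent dosing and classification of deviations. No endpoint definition, sample size or analysis is affected.

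**Working it through.** **Inputs.** Standard dose 25 mg daily, days 1-21, with adjustment below 60 mL/min (section 4.1.2). Moderate band 30-60 mL/min at 10 mg daily, days 1-21, and severe band below 30 at 15 mg every other day (Table 1b). Clearance equation (Appendix D).

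**Step 1: apply both rules as written.**

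| Clearance (mL/min) | Section 4.1.2 | Table 1b | Agree? |
|---|---|---|---|
| 29.9 | adjust, see Table 1b | 15 mg every other day | yes |
| 30 | adjust, see Table 1b | 10 mg daily | yes |
| 59 | adjust, see Table 1b | 10 mg daily | yes |
| 59.9 | adjust, see Table 1b | 10 mg daily | yes |
| **60** | **25 mg daily** | **10 mg daily** | **no** |
| 60.1 | 25 mg daily | not listed, so 25 mg | yes |
| 61 | 25 mg daily | not listed, so 25 mg | yes |

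**Step 2: size of the difference at 60.** Section 4.1.2: 25 × 21 = 525 mg per cycle. Table 1b: 10 × 21 = 210 mg per cycle. Ratio 525 / 210 = 2.5.

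**Step 3: can exactly 60 occur?** Read the male equation in Appendix D as (140 − age) × weight / (72 × creatinine). The printed bracket, taken literally, would subtract age × weight from 140 and give a negative value for any adult, so this is the only workable reading. A man of 68 years, 60 kg, creatinine 1.0 mg/dL: (140 − 68) × 60 / (72 × 1.0) = 4320 / 72 = 60.0. So it can.

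**Step 4: effect of rounding.** If clearance is recorded in whole numbers, every value from about 59.5 to 60.5 reads as 60 and meets the conflict. Rounding also moves patients across the line. Unrounded, 59.7 gives 10 mg in both places and 60.3 gives 25 mg in both; rounded to 60, each gives 25 mg in one place and 10 mg in the other.

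**Step 5: how often (illustration only).** The documents give no distribution of clearance. Assume whole-number recording and a normal distribution. The share of checks reading 60 is then the probability of 59.5-60.5:

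- mean 65, SD 20: 0.0193
- mean 70, SD 20: 0.0176
- mean 75, SD 25: 0.0133
- mean 80, SD 25: 0.0116

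If 20 patients each complete 13 cycles there are 20 × 13 = 260 checks, and the expected numbers are 5.0, 4.6, 3.5 and 3.0.

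**The case against.** The strongest reply is that the protocol already names the operative table. Section 4.1.2 defers to Table 1b for particulars, the footnotes to Table 1b and to the Time and Events table both base adjustment on Table 1b, and both give a query route to the Lead PI. A site that opens the table at each cycle will act consistently. This stands as mitigation. It does not settle the matter, because 4.1.2 is the passage that says who needs adjustment. A reader who starts there with a value of 60 has no reason to go on to the table, and nothing states that the table overrides the text.

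It is also fair to say that without rounding a value of exactly 60 is rare, and that the illustrative count rests on assumptions. Early discontinuation would lower 260, while accrual of up to 35 patients could raise it, so 260 is neither an estimate nor a bound.

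Three stronger readings are tempting, and the documents do not support them.

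- **That Amendment 10 announced an alignment and failed to deliver it.** Its reason, "Clarifies language to align with the contents of Table 1b", goes on to explain that the table sets out both dose and schedule. The listed changes add the words *and schedule* to the sentence and to the table heading, and the current text carries both. The entry does not claim that the clearance cut-offs were aligned.
- **That Amendment 6 shows the error.** Its entry "Discrepancy – CrCl = 30" records a different boundary, which was found and corrected. It shows that the sponsor has thought a single-value ambiguity worth fixing, but it is no evidence about 60.
- **That one of the two doses is an overdose under section 7.2.7.** That section measures overdose against the dose assigned to the individual patient, so a patient assigned 25 mg who takes 25 mg is not clearly over it. The lower dose could never be an overdose against the higher.

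**Conclusion.** The contradiction is real and can be read from the current text of section 4.1.2 and Table 1b alone: at 60 mL/min one leaves 25 mg daily and the other gives 10 mg daily, 525 mg against 210 mg per cycle. It is an internal inconsistency of narrow scope and low severity. Without rounding it touches one value. With whole-number recording, which is assumed, it touches a band about 1 mL/min wide. The figure of about 3 to 5 checks in 260 is illustrative only: it depends on an assumed normal distribution, assumed means and SDs, whole-number recording and full completion of 13 cycles by 20 patients. The finding does not depend on that figure or on the amendment history, and it implies no judgement on which dose or cut-off is right.

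**What to change.** Reconcile section 4.1.2 and Table 1b so that 60 mL/min falls on the same side in both. Which side is a clinical decision for the sponsor. In the same edit, state the precision to which the calculated clearance is recorded and whether the cut-off is applied before or after rounding, since that decides how values between about 59.5 and 60.5 are treated. The cost is about one symbol in one of the two places and one sentence on rounding. No change to the design, sample size or analysis is needed.
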